5.2.1.2. Additional Information for Male Subjects

Male subjects defined as subjects capable of producing sperm should be encouraged to advise any person of childbearing potential who are their sexual partners to use a highly effective method of contraception in addition to the subject's use of barrier contraception. A female condom and male condom should not be used together.

Subjects who are planning to donate sperm during the study period are excluded. If a subject is capable of producing sperm and withdraws early from the study, they should be advised not to donate sperm for at least 30 days after they received the single dose of study drug at Day 1/Dosing Session (Visit 3B). Additionally, male subjects who withdrawal early from the study should continue use of barrier contraception for a minimum of 30 days.

5.2.2. Nicotine Use

As changes in the consumption of nicotine may impact anxiety symptoms and/or mood, subjects should avoid starting, stopping or altering the use of these products from the time of providing informed consent until the End of Study. Due to the length of Day 1/Dosing Session, subjects are not permitted to smoke cigarettes/vape during the dosing session. Due to the possibility of nicotine withdrawal symptoms, subjects who are current users of nicotine products will be permitted to use nicotine replacement gum or patches. The dose and frequency of the nicotine replacement products will be determined by the subject's current level of dependence in accordance with the product's prescribing information.

5.2.3. Non-Medicinal Therapies

Any form of non-medicinal therapy should be stable 3 months prior to screening with no plans to start, stop or alter the use of non-medicinal therapies/activities (e.g., psychotherapy, acupuncture, hypnosis, or other similar therapy) from the time of providing informed consent until End of Study.

Non-medicinal therapies will be recorded in the eCRF, beginning at the time of ICF signing until End of Study (Week 12 [Visit 9] or Early Withdrawal).

5.3. Screen Failures

Screen failures are subjects who consent to participate in the clinical study but are never randomized.

Clinical Study Protocol: MMED008

Subjects excluded during screening should promptly be reported as a screen failure in the electronic data capture (EDC) system.

Subjects excluded during screening may be rescreened once in consultation with the Sponsor's Medical Monitor, when the reason for meeting an exclusion is likely to resolve (e.g., the subject had an exclusionary acute infection that is resolving, transient lab abnormalities, or a medication taper is taking longer than 30 days). Subjects who do not meet criteria for inclusion at screening or baseline on the HAM-A score are not permitted to rescreen. If a subject is rescreened, the subject must be reconsented to participate in the study, and all screening procedures should be repeated (unless the Investigator and Sponsor's Medical Monitor agree with re-using one or more original screening results).

Page 51

Clinical Study Protocol: MMED008

6. STUDY DRUG AND CONCOMITANT THERAPY

6.1. Description of Study Drugs

For the purposes of this protocol, the term "investigational drug" refers to MM-120 (25, 50, 100 or $200\,\mu g$ freebase-equivalent); the terms "study treatment" and "study drug" are interchangeable and refer to either MM-120 or matching placebo.

All study drugs will be supplied as a solid dosage form (capsules). Table 4 provides a description of the study drugs.

Table 4: MMED008 Study Drugs

Study Drug	Total Dose ^a (Freebase- equivalent)	Frequency; Route of Administration; Product Description	Use
MM-120	25, 50, 100 or 200 μg	Single dose; oral; capsule containing 25 µg MM-120 (D-LSD D-tartrate) freebase-equivalent blended with "generally recognized as safe" (GRAS) excipients	Investigational product
Placebo	Not applicable	Single dose; oral; capsule containing GRAS excipients	Blinding

Each subject will receive a total of 8 capsules (combination of active and/or placebo) to provide their randomly assigned total dose as follows:

6.2. Directions for Administration of Study Drug

Study drug (MM-120 25, 50, 100 or 200 µg freebase-equivalent or placebo) will be administered under blinded conditions. To maintain the blind, all subjects will receive a total of 8 capsules, which will be a combination of active capsules each containing 25 µg MM-120 freebase-equivalent and/or placebo capsules, depending on the subject's randomized dose (see Table 4). All 8 capsules will be taken together as the subject's single dose of study drug. Administration of study drug will occur only during Day 1/Dosing Session (Visit 3B), as specified in the Schedule of Activities (Table 2).

Subjects will take the 8 study drug capsules orally with ad libitum water. Subjects will only have 15 minutes to swallow all 8 capsules. Administration of study drug will be witnessed by the Investigator and/or Dosing Session Monitor(s), and the subject will subsequently be monitored at all times until released from the clinic by the study site designated physician, as detailed in the Dosing Session Monitor Manual.

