6.4.1. Unblinding

In the event of a medical emergency where knowledge of subject's study drug assignment is necessary per the medical judgment of the Investigator, the Investigator may break the blind using the randomization system. If possible, the Sponsor's Medical Monitor should be notified before the Investigator breaks the blind to discuss the case. If not possible, the Sponsor's Medical Monitor should be notified as soon as possible after breaking a treatment code. The unblinding must be clearly justified and explained by a comment in the source documentation, along with the date on which the code was broken and the identity of the person authorizing the unblinding.

Only the Investigator or delegate should be unblinded to the subject's code. Site personnel and Sponsor personnel directly associated with the conduct of the study should not be unblinded.

Additionally, the Sponsor's delegate may unblind the treatment for an individual subject's serious adverse event (SAE) if needed to fulfill expedited regulatory reporting requirements, or the Safety Review Committee (SRC) may have access to the treatment code, if needed.

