6.8. Study Drug Compliance

All subjects will be dosed at the site and will receive study drug directly from the Investigator or designee under medical supervision; the study drug administration will be witnessed by the Investigator and/or Dosing Session Monitor(s). The date and time of study drug administration at the site will be recorded in the source documents and the eCRF.

The randomized study drug and study subject identification will be confirmed at the time of administration by a member of the study site staff other than the person administering the study drug. The study site personnel administering the dose will examine the subject's mouth and hands to ensure that the study drug was ingested.

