Drug Class or Drug Name	Washout Conditions/ Prohibition Period ^a	Allowable Conditions
Benzodiazepines	Last dose must have been taken at least 5 half-lives prior to Day 1/Randomization (Visit 3A)	To treat anxiety during Day 1/Dosing Session (Visit 3B), at Investigator's discretion ^b
Lithium	Last dose must have been taken at least 7 days prior to Day 1/Randomization (Visit 3A)	None
Monoamine oxidase inhibitors (MAOIs) ^c	Last dose must have been taken at least 3 weeks prior to Day 1/Randomization (Visit 3A)	None
Antipsychotics – traditional		
Antipsychotics – atypical	Last dose must have been taken at least 5 half-lives prior to Day 1/Randomization (Visit 3A)	None
Atypical agents (e.g., bupropion, mirtazapine)		
Barbiturates Selective serotonin reuptake inhibitors (SSRIs). NOTE: fluoxetine washout is 35 days		
Serotonin-norepinephrine reuptake inhibitors (SNRIs)		
Serotonin–norepinephrine–dopamine reuptake inhibitors (SNDRIs)		
Serotonin modulators (e.g., vortioxetine, trazodone)		
Tricyclic antidepressants (TCAs)		
Stimulant (e.g., methylphenidate hydrochloride)		
Cannabis ^d	Prohibited from Baseline (Visit 2) through End of Study	None
Other medications, supplements, or therapeutics that affect serotonergic function (e.g., efavirenz, Kava, ginkgo biloba, St. John's Wort, 5-hydroxytryptophan [5-HTP], ayahuasca, dimethyltryptamine [DMT])	Last dose must have been taken at least 5 half-lives prior to Day 1/Randomization (Visit 3A)	None

Note: This table is not a comprehensive list of all restricted medications or supplements. Consult the Sponsor's Medical Monitor or designee with any questions about specific medications, supplements or therapeutics.

- ^a Subjects on prohibited medications, supplements or other therapeutics at the time of Screening may taper off that substance(s) prior to Baseline (Visit 2) (see Section 8.1.6) and will be eligible to participate in the study if the required washout conditions have been met. Investigator must consider the half-life of active metabolites.
- Benzodiazepines should only be offered and administered if non-pharmacological interventions (e.g., reassurance, verbal communication) do not adequately address severe anxiety during the Dosing Session.

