8.4.4. Montgomery-Åsberg Depression Rating Scale (MADRS)

The MADRS will be administered during the study at the visits indicated in the Schedule of Activities (Table 2). The MADRS takes approximately 15-20 minutes to administer.

An appropriately trained/qualified central rater located remotely from the site will be used to administer and score the MADRS, as was described for the HAM-A (see Section 8.4.3,

including plans for completing a safety report risk assessment, reporting AE, SAE, and/or AESIs suggestive of abuse potential to the site, and immediately contacting the site in case of any emergent risk to the subject's safety). As much as possible, the MADRS should be administered at approximately the same time of the day across each of the individual subject's study visits. The MADRS will be administered by the central rater after completion of the HAM-A.

The MADRS is used to assess depression severity and to detect changes due to antidepressant treatment (Montgomery & Åsberg 1979). This questionnaire includes 10 clinician-completed items.

Each of the 10 questions is scored with a range of 0-6 points. An item score of 0 indicates item not present or normal, while an item score of 6 indicates severe or continuous presence of the symptoms. The total possible score is 60, and higher scores represent a more severe condition. A decrease in score by $\geq 50\%$ indicates a response to treatment, and an actual score of ≤ 10 indicates a remission of symptoms.

8.4.5. Clinical Global Impression – Severity (CGI-S) and Clinical Global Impression – Improvement (CGI-I)

The Clinical Global Impression (CGI) scales will be administered during the study at the visits indicated in the Schedule of Activities (Table 2). Sites should make every effort to maintain the same rater for the same subject for the CGI-S/I. The CGI-S/I rater may not function as a DSM or the study site designated physician as they may be functionally unblinded on dosing session day.

CGI-S: The CGI-S scale will be used to assess the subject's current severity of illness at the time of the assessment relative to the clinician's past experience with patients who have the same diagnosis (Guy 1976). The CGI-S comprises 1 Investigator-completed (or trained rater-completed) item with 7 possible ratings (1-7 points), where a higher score indicates more severe illness.

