All AEs, whether or not related to the study drug treatment, must be fully and completely documented on the adverse event case report form and in the subject's source documents. In addition, any AE resulting in permanent treatment discontinuation must be recorded on the appropriate case report form as well as documented in the subject's source documents. AE terms should include a diagnosis, as available, in preference to listing the individual signs and symptoms. If the diagnosis is not known, the Investigator should record each sign and symptom as an individual AE.

AEs should be reviewed by a PI/Sub-I or Study Site Designated Physician.

Overdose and pregnancy in the subject or subject's partner will be reported as described in Section 9.9 and Section 9.10, respectively.

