## 6.3.3 Change from Baseline in CGI-S

The CGI-S assesses the subject's current severity of illness at the time of the assessment, as assessed by the clinician and in reference to the clinician's past experience with patients having the same diagnosis. The CGI-S consists of one investigator-completed rating ranging from 1 (normal, not at all ill) to 7 (among the most extremely ill patients); a higher score indicates a more severe illness.

Descriptive statistics, including 95% CIs for the mean, will be presented for actual values and change from Baseline for scheduled visits. The change from Baseline difference in means between each dose of MM-120 and placebo, 95% CI for the difference and corresponding p value from a two-sample t-test will be presented for Day 2, Week 1, Week 2, Week 4, Week 8 and the End of Study visit. A by-subject listing of results by visit, including any unscheduled visits, will be provided.

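### The rule keeping functionally unblinded staff from rating CGI-S/I leaves out an Investigator who is neither a DSM nor the site-designated physician, although that Investigator is a named CGI rater with knowledge of dosing-day events

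*Protocol*

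**What the plan says.** **Who rates the CGI.** Protocol 8.4.5: "The CGI-S comprises 1 Investigator-completed (or trained rater-completed) item"; CGI-I has the same pair of permitted raters. SAP 6.3.3 is narrower: "The CGI-S consists of one investigator-completed rating". SAP 6.3.4 words CGI-I the same way, and neither SAP section mentions a trained rater. Section 8.4.5 also asks sites to keep one CGI rater per subject. Both scales are first rated after dosing on Day 2 (Table 2).

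**Who is barred.** Protocol 8.4.5: "The CGI-S/I rater may not function as a DSM or the study site designated physician as they may be functionally unblinded". The bar covers the dosing session monitors (DSMs) and the site-designated physician, and nobody else.

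**What the Investigator does.**
- Section 9.7 has the Investigator determine the severity of each adverse event (AE). Section 9.3 has the PI or a designee classify events of special interest (AESIs), whose terms include hallucination and euphoric mood. Section 9.4: "AEs should be reviewed by a PI/Sub-I or Study Site Designated Physician".
- Table 5 allows benzodiazepines "To treat anxiety during Day 1/Dosing Session (Visit 3B), at Investigator's discretion".
- Section 6.4.1 lets the Investigator break a subject's code in a medical emergency, and then "Only the Investigator or delegate should be unblinded to the subject's code".
- Section 6.2: "Administration of study drug will be witnessed by the Investigator and/or Dosing Session Monitor(s". Section 6.8: subjects "will receive study drug directly from the Investigator or designee under medical supervision".

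**The concern.** The reason 8.4.5 gives for its bar is what a person may learn on dosing day, but the bar is written as a list of two job titles. An Investigator outside those titles can learn much the same things and remains a named rater. Protocol 2.3 expects perceptual effects at the higher doses, so a rater who has graded or classified such events has a good clue to the dose group.

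CGI-S and CGI-I are clinician-judged, and SAP 6.3.3 and 6.3.4 test each dose against placebo with a p-value at every visit from Day 2. SAP 4.6 applies no multiplicity adjustment to them, and SAP 8 puts CGI-S through Week 4 in the top-line analysis. A rater influenced by visible drug effect could produce an apparent dose trend that would be read as clinical support for the HAM-A result.

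**Working it through.** The documents give no figure to reproduce. The main check is to compare the roles.

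**Step 1. Roles side by side**

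| Role | Route to knowledge of the session | Barred from CGI by 8.4.5? |
|---|---|---|
| DSM | Observes throughout (8.6.3) | Yes |
| Site-designated physician | On call (8.6.3), release checklist (8.6.4), neuropsychiatric exams (8.2.2) | Yes |
| Investigator holding neither role | Grades AEs (9.7), may classify AESIs (9.3), may decide on session benzodiazepines (Table 5), may break a code (6.4.1) | No |

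**Step 2. Can the third row exist?** Yes. Section 9.4 and exclusion 26j list the Investigator and the site-designated physician as alternatives. Section 8.3.2 makes laboratory review by the PI or Sub-I conditional on a medical degree, so a non-physician PI is foreseen. An Investigator who also acts as DSM or site physician is already barred.

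**Step 3. Does another provision close the gap?** Section 6.4 keeps the Investigator unaware of assignment, but that is the formal blind and does not limit knowledge of how the session went. Section 6.4.1 does not call for a new CGI rater after a code break, and 8.4.5 favours keeping the same one. No section keeps a CGI rater away from AE or rescue records.

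**Step 4. Illustration of size.** From the documents: 36 per arm and a two-sample t-test (SAP 9, 6.3.3). Assumed: no true effect, two-sided 5% level, SD of CGI-S change 1.0 to 1.4, rater bias *b* of 0.25 or 0.5 point favouring active drug, and a fraction *f* of the active-arm subjects in the comparison rated with that bias.

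Degrees of freedom = 36 + 36 − 2 = 70; critical value 1.994; noncentrality = *f*·*b* / (SD·√(2/36)).

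Example with *f* = 1, *b* = 0.25, SD = 1.0: 0.25 / 0.2357 = 1.061, giving a rejection probability of 18.2%.

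| *f* | *b* | SD 1.0 | SD 1.2 | SD 1.4 |
|---|---|---|---|---|
| 1 | 0.25 | 18.2% | 14.1% | 11.6% |
| 1 | 0.5 | 55.3% | 41.4% | 32.1% |
| 0.25 | 0.25 | 5.8% | 5.6% | 5.4% |
| 0.25 | 0.5 | 8.2% | 7.2% | 6.6% |
| 0.10 | 0.5 | 5.5% | 5.4% | 5.3% |

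These are two-sided rejection rates for one dose-placebo test, and the nominal rate is 5%. The calculation treats the bias as a shift in the mean difference. The documents give no value for *f*, *b* or the SD.

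**The case against.** The strongest reply is that the people who watch the session are already barred, and that the remaining routes are narrow. Much of this stands.

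- **Witnessing.** A reader might infer from 6.2 that an Investigator who witnesses dosing is unblinded. The text does not support that. The witness sees eight capsules swallowed within 15 minutes, identically packaged (6.4), before any effect, and a DSM may witness instead.
- **Rescue.** Table 5 leaves session benzodiazepines to the Investigator. Appendix 3 gives the choice and administration of rescue medication to the site-designated physician, who is already barred. The two passages conflict and must be reconciled. Until then, Table 5 alone does not show that a CGI rater decides on rescue.
- **Code breaks.** These are for a medical emergency in a single subject. They could not plausibly create a dose trend across arms of 36.
- **AE grading.** This is second-hand knowledge, but 9.7 assigns it to the Investigator for every event. It is the firmest remaining route and the objection does not remove it.
- **Trained rater.** The protocol allows one, so exposure may be partial or nil. But it does not require one, and the SAP does not mention one. The SAP sentences describe the scale rather than delegate raters, so they are supporting evidence only.
- **Other documents.** The Dosing Session Monitor Manual is not available here, and it could contain a rater firewall.
- **Reach.** Protocol 10.2.2.4 calls these endpoints descriptive. Functional unblinding is acknowledged (2.4), and subjects' guesses are collected on Day 2 (8.5.4). That question measures the subject's belief and not the rater's.

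**Conclusion.** The gap is real and sits in 8.4.5: the plan permits functionally unblinded CGI rating by an Investigator who is neither a DSM nor the site-designated physician. The documents do not say how many sites have such an Investigator, or whether that person would rate.

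Two stronger readings are not supported. One is that CGI ratings will be unblinded; they need not be, because a trained rater is allowed. The other is that the efficacy conclusion is at risk. HAM-A, which carries the primary and key secondary endpoints, and MADRS are scored by remote central raters (8.4.3, 8.4.4), so the confirmatory tests are unaffected. The exposure is confined to CGI-S and CGI-I, and in the top-line analysis to CGI-S.

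The rates of 12% to 18% (0.25 point) and 32% to 55% (0.5 point) are upper-bound illustrations. They assume that every active-arm rating in the comparison carries the full bias, and an SD that the documents do not give. With a quarter of ratings affected they fall to 5.4% to 5.8% and 6.6% to 8.2%. The case for a change rests on the incomplete rule, not on these figures. It is a cheap improvement.

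**What to change.** 1. **Protocol 8.4.5.** State that a subject's CGI-S/I rater may not be a DSM, the site-designated physician, or anyone who attended that subject's post-dose session, decided on session medication, graded or classified that subject's dosing-day AEs or AESIs, or broke that subject's code.
2. **Where the Investigator does any of these,** use the trained rater that 8.4.5 already allows. Alternatively, state in 9.7 that a Sub-I or the site-designated physician may grade dosing-day AEs. Section 9.4 is not enough for this, because it covers review, while 9.7 assigns grading to the Investigator.
3. **SAP 6.3.3 and 6.3.4.** Describe both scales as completed by the Investigator or a trained rater, under the same bar.
4. **Table 5 and Appendix 3.** Reconcile who decides on rescue medication during the session.

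The cost is a sentence in 8.4.5, a possible sentence in 9.7, the SAP wording and a check of each site's delegation log. At some sites the Investigator must give up either CGI rating or dosing-day AE grading. The bar reduces the problem but does not remove it: CGI rating starts on Day 2, and a subject may still describe the session to the rater.

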6.3. Randomization

Once final eligibility is confirmed at Day 1/Randomization (Visit 3A), subjects will be randomized centrally. The assigned randomization number will be used to identify the study drug to be dispensed to the subject and will be entered into the EDC system.

Subjects randomized to a total dose of 25 μ g receive 1 active capsule + 7 placebo capsules.

Subjects randomized to a total dose of 50 µg receive 2 active capsules + 6 placebo capsules.

Subjects randomized to a total dose of 100 μg receive 4 active capsules + 4 placebo capsules.

Subjects randomized to a total dose of 200 µg receive 8 active capsules.

Subjects randomized to placebo receive 8 placebo capsules.

Clinical Study Protocol: MMED008

There are 5 treatment groups to which subjects will be randomized in a 1:1:1:1:1 ratio:

- Arm A: 25 µg (freebase-equivalent) of MM-120 (n \approx 36)
- Arm B: 50 μ g (freebase-equivalent) of MM-120 (n \approx 36)
- Arm C: 100 µg (freebase-equivalent) of MM-120 (n \approx 36)
- Arm D: 200 µg (freebase-equivalent) of MM-120 (n \approx 36)
- Arm E: Placebo ($n \approx 36$).

6.4. Blinding

A double-blind/masking technique will be used. All doses of MM-120 and placebo will be packaged identically so that treatment blind/masking is maintained. The subject, the Investigator, and Sponsor personnel or delegate(s) who are involved in the treatment or clinical evaluation of the subjects will be unaware of the treatment group assignments.

At the end of the study and after medical/scientific review has been performed and data have been declared final and complete, the official, final database will be frozen and unblinded. The Sponsor will be granted access to the frozen and unblinded database in order to analyze the data.

